### 9.2 Secondary Efficacy Analyses

The outcomes for Aims 3, 4 and 5 in Section 4 are assessed at multiple time points throughout the study.

**Aim 3.** Outcome (a) WOMAC-C is assessed at baseline and each study visit through week 24. Outcome (b) HADS (anxiety and depression scales which will be modeled separately) is assessed at in-person visits except baseline. Outcome (c) PGIC is assessed at week 3 and week 24 only. Outcome (d) PROMIS Sleep Disturbance Scale – 6A is assessed at baseline and at in-person visits through week 24. Outcome (e) Sleep Duration Question is assessed at baseline and week 24 only. Outcome (f) Daily NRS is collected daily for the week prior to each study visit and these daily NRS values will be modeled in the analysis. The analysis plan for outcomes (a), (b), and (d), and (f) will be similar to the analysis for aim 2 except that the model will adjust for possible carryover effects in placebo-treated periods that are preceded periods with the active drug treatment. To incorporate the modeling of carryover effects, we will use a modification of model (1):

$$y_{i(s)jkm} = \beta_0 + \gamma_j + \delta_k + \beta_1 X_{i(s)jk} + \lambda_{drg} Z_{i(s)jk,drg} + \beta'_2 \mathbf{w}_{i(s)} + b_s + b_{i(s)} + \epsilon_{i(s)m}, \quad (2)$$

where  $\lambda_{drg}$  is used to model carryover effects with  $Z_{i(s)jk,drg} = 1$  if the treatment at block  $j$ , period  $k - 1$  is drug for patient  $i(s)$  in site  $s$ ; all other terms in the model are defined as in (1). Hypothesis 4 for these measures correspond to  $H_0 : \beta_1 = 0$  versus  $H_a : \beta_1 \neq 0$  from model (2).

For PGIC, this instrument asks if the overall pain since the start of the study is “Very much improved” (score 0), “Much improved” (score 1), “Minimally improved” (score 2), “No Change” (score 3), “Minimally worse” (score 4), “Much worse” (score 5), “Very much worse” (score 6). The analysis for outcome (c) PGIC will use a proportional odds regression with outcome PGIC at week 24 (V9), controlling for treatment, age, sex and baseline WOMAC-A; this model will not control for week 3 PGIC since the instrument is asking about the change in pain. Note also that the treatment in the last period is the same treatment as in the first period, so a comparison of the active to the placebo in terms of change in pain can be done using week 24 PGIC outcomes for the two different treatment sequences used in this trial. The analysis plan for outcome (e) will follow the same approach as in aim 4 below.

**Aim 4.** Outcomes (a)-(f) are assessed at baseline and week 24. Testing hypotheses for these outcomes will not benefit from the multi-period crossover design because they are assessed only at baseline and week 24. Instead, we will test the hypotheses by comparing subjects taking active drug versus placebo at the last treatment period ending on week 24. Regressions will be used to model the outcome at week 24 as a function of treatment, the baseline level of the outcome, age, sex and K-L Grade. A standard linear regression will be used for continuous outcomes; a proportional odds model will be used for the non-binary ordinal outcomes defined by discrete categories (e.g., PHQ-2, GAD) and logistic regression models will be used for binary outcomes (e.g., OUQ).

**Aim 5:** The hypotheses under aim 5 are for staircase-evoked pain assessment, serum and synovial fluid levels of chemokines and cytokines; and synovial monocyte chemoattractant protein-1/CCR-2 receptor binding inhibition in blood and synovial fluid. Hypotheses for Staircase-Evoked Pain Assessment, will be tested with the same approaches as for testing the hypotheses under Aim 3 which can accommodate outcomes on participants measured at more than one occasion. For synovial fluid, which is only collected once, the hypothesis testing will use the same approach as for hypotheses under Aim 4 - we will model the week 6 assessment of measures as functions of treatment in the first period, adjusting for sex, age and K-L Grade. The analysis for serum chemokines/cytokines will be more complicated since these measures are obtained at multiple occasions and we want to assess if their impact on pain differs due to treatment in this multi-crossover study. Analytical methods for this complex type of mediation analysis still need to be developed. We will evaluate the impact of the treatment sequence on the change in the WOMAC-A from baseline to V9, modeling serum and synovial fluid levels of chemokines and cytokines as potential mediators of treatment effect by investigating a generalization of the  $2 \times 2$  crossover mediation modeling approaches introduced by (Josephy *et al.*, 2015) and generalized to this multi-crossover trial design.

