3. Daily Knee Pain Intensity on a 0-10 Numeric Rating Scale (NRS). Pain intensity is reported by patients with chronic pain as one of the most important targets of treatment, and daily pain intensity ratings are a recommended core outcome measure for clinical trials of treatments for chronic pain. Daily ratings are preferable to ratings of recalled pain over longer time periods such as a week, as daily ratings minimize the influence of recall biases (Dworkin et al., 2005). Subjects provide one-daily reports (at the end of the day) of their

average knee pain intensity on a 0-10 pain intensity NRS over the course of a week, and those daily ratings are averaged to compute a mean knee pain intensity score.

4. HADS (Hospital Anxiety and Depression Scale). The HADS is a 14-item self-report questionnaire designed to assess symptoms of anxiety and depression in those with medical illness (Norton et al, 2013). It has well-established reliability and validity in the assessment of symptoms of depression and emotional distress, and it has been used in numerous clinical trials. It does not include somatic symptoms, such as fatigue and sleeplessness, which may otherwise be attributable to physical illness, and it has been standardized among large community samples. It has also been validated in several medical illness populations with good sensitivity and specificity for predicting DSM-IV major depression or generalized anxiety disorder diagnoses. The HADS has been recommended as a psychosocial phenotyping measure in clinical trials of treatments for chronic pain (Edwards et al, 2016).
5. Staircase-Evoked Pain Assessment: This procedure consists of stepping fully up and down onto an 8in (20.32cm) high platform with both feet a total of 24 times. The lead leg is alternated between each up/down cycle. Subjects are instructed to use their normal gait for completing this task and are encouraged to complete the task despite increasing pain, without stopping if possible. The procedure is timed, and current knee pain intensity on a 0-10 NRS is assessed immediately before and following the procedure while the subject is in a seated, resting position.

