The following are secondary physiological outcomes related to pain and potential exploratory biomarkers for pain and treatment response.

- Staircase-evoked pain assessment. This procedure consists of stepping fully up and down onto a 20 cm high platform with both feet a total of 24 times. The lead leg is alternated between each up/down cycle. Subjects are instructed to use their normal gait for completing this task and are encouraged to complete the task despite increasing pain, without stopping if possible. The procedure is timed, and current knee pain intensity on a 0-10 Numeric Rating Scale (NRS) is assessed immediately before and following the procedure while the subject is in a seated, resting position. This staircase-evoked pain assessment has been well tolerated in multiple studies of knee OA participants to date, and the standardized effect size for anti-inflammatory treatments was shown to be considerably higher with the staircase measure than with other measures such as pain intensity ratings (Treister *et al.*, 2019).
- Temporal profile of OA pain will be assessed using the NRS (integer scale from 0-10) at the end of the day for the first seven days following the Screening visit in order to obtain a measure of pain variability **which will be used to screen out individuals with high variability (SD > 1.2) in their pain.** Additionally, after Baseline, the NRS will be completed daily for the seven days immediately preceding all study visits.
- Serum levels of cytokines and chemokines. A specific list is provided in the Appendix of the protocol.
- Monocyte chemoattractant serum protein-1(MCP-1)/CCR-2 receptor binding inhibition by CNTX-6970. This test provides as a single score, expressed as a percentage, 0-100%, with higher scores indicating more binding inhibition.
- Monocyte chemoattractant protein-1 (MCP-1)/CCR-2 receptor binding inhibition by CNTX-6970 in synovial fluid.
- Synovial fluid levels of cytokines and chemokines (a specific list is provided in Appendix of the protocol), assessed at the end of the first treatment period (week 6) which will allow a comparison of subjects treated with CNTX-6970 300 mg BID to placebo-treated subjects.

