## 7 General Analysis Considerations

All demographic and baseline variables will be summarized by means, standard deviations, medians, and interquartile ranges (IQR) for continuous measures. Frequency and percentages will be reported for all categorical measures (including binary measures).

The general approach for statistical inference for aims associated with outcomes measured at multiple periods will utilize a mixed-effects multi-period crossover model with 2 blocks and 2 treatment periods per block (of length 6 weeks). Maximum likelihood estimation will be used primarily for parameter estimation and likelihood ratio tests will be used to test hypotheses under the primary and secondary objectives. Significance of an active treatment effect versus placebo will be determined by testing if the treatment effect coefficient differs from zero in the mixed-effect model. When there is a possibility of carryover effects, the multi-crossover model will incorporate carryover effect terms. Only carryover effects from active to placebo will be formally modelled. For outcomes recorded only at baseline and week 24, an appropriate generalized linear model will be used to estimate and test for the active treatment effect, controlling for covariates noted below and also the baseline value of the outcome.

All hypothesis tests will be two-sided using  $\alpha = 0.05$  significance level, and  $p$ -values unadjusted for multiple testing will be reported. The justification for this decision is that this is Phase II investigation and all assessed outcomes are of specific and unique interest. Much more important than testing hypotheses is the efficient estimation of all quantities of interest, and this will be carried out throughout the analyses. Treatment effect point estimates with 95% confidence intervals will be reported along with estimates of other model parameters, regardless of whether the null hypotheses were rejected or not.

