### 9.1 Primary Efficacy Analysis

For the efficacy Aim 2, data from the WOMAC Part A (WOMAC-A) assessed only in the last two weeks of each 6-weeks treatment period will be used for this primary analysis in order to avoid any carryover effects, which are expected to vanish after 4 weeks. Hypothesis 1 in Section 4 will be tested using the following random-effects multi-period crossover model that employs block and period effects to compare the active treatment to placebo (Zucker *et al.*, 1997; Chen and Chen, 2014). Specifically, the model is:

$$y_{i(s)jkm} = \beta_0 + \gamma_j + \delta_k + \beta_1 X_{i(s)jk} + \beta_2' \mathbf{w}_{i(s)} + b_s + b_{i(s)} + \epsilon_{i(s)m}, \quad (1)$$

where  $i(s)$  is the index for patient  $i$  at site  $s$ ;  $\beta_0$  is the intercept;  $j$  is the index for block,  $j = 1, 2$  and  $\gamma_j$  is the block effect;  $k$  is the index for period,  $k = 1, 2$ , and  $\delta_k$  is the period effect;  $m$  is the measurement time;  $y_{i(s)jkm}$  is the primary outcome for subject  $i(s)$ , block  $j$ , period  $k$ , time  $m$ ;  $\beta_1$  represents the treatment effect, and  $X_{i(s)jk}$  is an indicator for active treatment ( $X_{i(s)jk} = 1$ ) or placebo ( $X_{i(s)jk} = 0$ ) for patient  $i(s)$ , in block  $j$ , during period  $k$ ;  $\mathbf{w}_{i(s)}$  is a vector of baseline characteristics (e.g., age, sex, K-L grade indicator) for patient  $i(s)$  and  $\beta_2$  is a vector of coefficients for those baseline characteristics;  $b_s \sim N(0, \sigma_{site}^2)$  is a random site effect and  $b_{i(s)} \sim N(0, \sigma_b^2)$  is a subject-level random effect (nested within site);  $\epsilon_{i(s),m}$  is a random error with an  $AR(1)$  structure:  $\epsilon_{i(s),m} = \phi \epsilon_{i(s),m-1} + u_{i(s)m}$ , with  $u_{i(s)m} \sim N(0, \sigma_u^2)$ . The subject-level random effects will model the repeated measures within subjects. The block and period effect terms will accommodate changes in mean pain scores across blocks and periods of the design.

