The primary hypothesis of interest for this model is  $H_0 : \beta_1 = 0$  versus  $H_a : \beta_1 \neq 0$ . Maximum likelihood estimation will be used to estimate the model parameters using the statistical software R and likelihood ratio tests will be performed to test and obtain  $p$ -values for the hypotheses of treatment effects (active versus placebo) for the active treatment. Under the null hypothesis, the likelihood ratio test will have an approximate chi-square distribution with 1 degree of freedom. The hypothesis testing proposed here is based on the WOMAC-A assessed only in the last 2 weeks of each 6-week treatment period. This provides a more than adequate 4-week washout interval for CNTX-6970. The adequacy of this 4-week period is based on extensive pharmacokinetics (PK) and pharmacodynamics (PD) of the study agent CNTX-6970 provided in the Centrexion dossier.

Additionally, for the analysis under Aim 3 described below, we explicitly model the potential carryover effects using model (2),

The proposed model (2) utilizes a standard approach to adjust for carryover effects in a multi-period crossover design when estimating the treatment effect, and allows for testing for the existence of carryover effect (Chen and Chen, 2014).

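### The SAP's model for daily NRS pain has no subject-by-period term and uses daily values where the protocol uses weekly means, so the test of Hypothesis 2(f) is too liberal if patients' levels shift between periods or weeks

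*SAP*

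**What the plan says.** Protocol F.2.4, item 3, defines the measure: patients rate average knee pain each evening for a week, and "those daily ratings are averaged to compute a mean knee pain intensity score".

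SAP 4.4.3 gives the schedule after Baseline: "the NRS will be completed daily for the seven days immediately preceding all study visits". With eight post-baseline visits three weeks apart, that is 14 ratings per 6-week period and 56 in all.

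SAP 9.2, Aim 3, outcome (f), takes the single rating as its unit: "these daily NRS values will be modeled in the analysis". The analysis "will be similar to the analysis for aim 2 except that the model will adjust for possible carryover effects in placebo-treated periods" that follow active drug, which is model (2). Apart from the carryover term, model (2) takes its terms from model (1) in SAP 9.1. There the random terms are a site intercept and a subject intercept, and the residual "is a random error with an $AR(1)$ structure". On within-patient correlation the SAP says: "The subject-level random effects will model the repeated measures within subjects".

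SAP 7 sets the level: "All hypothesis tests will be two-sided using" 5%, with no multiplicity adjustment. The test is by maximum likelihood, and in SAP 9.1 "the likelihood ratio test will have an approximate chi-square distribution with 1 degree of freedom".

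**The concern.** Two things need attention.

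First, the documents use different units of analysis for the same outcome: a weekly mean in the protocol and daily values in the SAP.

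Second, model (2) can express only two kinds of within-patient correlation: a level constant over 24 weeks, and a correlation that dies away over days. It has no term for a patient whose level is a point higher throughout one period, or in one diary week. Treatment is constant within a period, so a period-long shift looks like a treatment difference for that patient, and the model counts the 14 ratings that share it as largely separate evidence.

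At stake are the standard error, confidence interval and p-value for Hypothesis 2(f). The outcome is the direct pain rating that sits beside WOMAC-A. SAP 7 ranks efficient estimation above testing, so intervals that are too narrow matter as much as false positives.

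**Working it through.** **Inputs from the documents.** Sequences Drug-Placebo-Placebo-Drug and Placebo-Drug-Drug-Placebo, 1:1 (SAP 5.3); 55 patients (SAP 6); 56 ratings per patient (SAP 4.4.3); model (2); two-sided 5%.

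**Assumed inputs.** Daily residual variance σe² = 1 and between-subject variance σb² = 3; day-to-day autocorrelation φ of 0, 0.3 or 0.6; subject-by-period variance σp² of 0-100% of σe²; subject-by-week variance σw² of 0-50%. Neither document gives any of these. Site and baseline covariates were left out, and diaries were complete.

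**Method.** The true covariance of two ratings from one patient on days d and d′ is

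σb² + σp²·[same period] + σw²·[same diary week] + σe²·φ^|d−d′|·[same diary week].

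Model (2) can fit only a constant plus a multiple of φ^|d−d′|. Take the closest such V to the true covariance Vt, minimising log|V| + tr(V⁻¹Vt). With A = ΣX′V⁻¹X and B = ΣX′V⁻¹VtV⁻¹X, the model variance of β₁ comes from A⁻¹ and the true variance from A⁻¹BA⁻¹. If r is model SE divided by true SE, then

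size = 2Φ(−1.96 r).

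**The plan's own figure first.** With σp² = σw² = 0 and AR(1) run on study day, r = 1.00 and size = 5.0%. Simulation of 800 trials at φ = 0.3 gives 5.1-5.6% over three ways of coding AR(1). The test keeps its level when the SAP's model is true.

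**With shifts** (large-sample size, AR(1) on study day):

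| Extra variance, % of daily | φ = 0 | φ = 0.3 | φ = 0.6 |
|---|---|---|---|
| None | 5.0% | 5.0% | 5.0% |
| Week only, 25 | 12.5% | 8.9% | 6.5% |
| Week only, 50 | 14.6% | 10.3% | 7.0% |
| Period, 10 | 16.2% | 11.7% | 8.6% |
| Period, 25 | 24.5% | 17.9% | 12.5% |
| Period, 50 | 29.9% | 22.8% | 16.1% |
| Period, 100 | 32.4% | 25.9% | 18.6% |

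Example: period variance 50%, φ = 0 gives r = 0.53; 1.96 × 0.53 = 1.039; 2Φ(−1.039) = 0.299. The model SE is then 47% too small. At φ = 0.6, r = 0.72, so it is 28% too small.

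**Simulation check** (φ = 0.3, three AR codings): period variance 10% gives 12.8-13.6%, 25% gives 16.8-18.6%, 50% gives 19.6-21.4% and 100% gives 22.8-26.4%. Week-only variance of 25% gives 7.6-9.5%, and 50% gives 11.2-14.8%. Monte Carlo error is √(0.05 × 0.95/800) = 0.8 points near 5% and √(0.2 × 0.8/800) = 1.4 points near 20%.

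**Diary gaps.** Diary weeks are separated by 14 days without ratings, and the SAP does not say how AR(1) treats them. If it runs on consecutive ratings and ignores the gaps, φ = 0.6 alone gives 8.9% with no extra variance. The largest size found, 32.7%, also comes from this coding (period variance 100%, φ = 0). Restarting AR(1) each period gives somewhat lower values, for example 13.3% at period variance 50% and φ = 0.6.

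**Candidate remedies:**

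- Daily values with a subject-by-period intercept: 4.5-6.5% (simulated).
- Weekly means with that intercept: 4.1-6.9% (simulated).
- Weekly means without it: 5.0% if the clustering is by week only, but 5.9-13.6% with period variance of 10-100% (large-sample).
- One diary-week mean per period: 5.0% throughout (large-sample).

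**The case against.** The strongest objection is that every size above 5% needs a variance that the documents do not supply. The nearest figure is the screening limit of 1.2 on the SD of daily ratings (SAP 5.2), which says nothing about shifts between weeks or periods. This stands. A reader might infer that the 5% test simply becomes a 20-29% test; the documents do not support that. Such values appear in only part of the range, mainly with period variance of 25-100% of daily variance and weak autocorrelation. Week-only variance of 25-50% stays at or below about 15% with AR(1) on study day.

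A reader might also blame the daily data as such. That does not hold: daily values with a subject-by-period term keep about 5%, while weekly means without it can reach about 14%. Nor does the SAP analyse a different quantity. With complete diary weeks, a linear model targets the same mean difference from daily ratings or their weekly mean; what differs is the unit of analysis.

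Whether all 56 ratings enter is an inference, since the Aim 3 analysis is only said to be similar to Aim 2, which uses the last two weeks of each period. With only the last diary week per period, size was still 5.9-26.2% across the scenarios with extra variance and the AR codings.

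Finally, this is one of six Aim 3 outcomes in a Phase II trial with unadjusted p-values, and the calculations do not bear on the primary WOMAC-A test. Both points stand and limit the severity.

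The objection does not show that the shifts are absent. The protocol's Background describes chronic pain with acute flares, and section G.5 allows acetaminophen and intermittent opioids as rescue. Some drift over 24 weeks is to be expected, though its size is unknown.

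**Conclusion.** The point holds as a conditional one. The mismatch in units is certain from the text, and so is the absence of a subject-by-period or subject-by-week term in model (2). The consequence runs one way: positive week or period shifts push the size above 5%. The amount rests on assumed variances: with AR(1) on study day and φ from 0 to 0.6, about 5% without shifts and up to about 30% at period variance of 50%, with about 33% the most found under any setting.

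For a sense of scale, suppose the daily SD were at the screening limit of 1.2, so the variance is 1.44. A 10% share is 0.144, a between-period SD of √0.144 = 0.38 points; a 50% share is 0.72, an SD of √0.72 = 0.85 points. Since interval coverage is one minus the size, nominal 95% intervals would cover about 84-91% of the time in the first case and 70-84% in the second.

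The cause is the missing random term; the choice of unit is a separate inconsistency to reconcile. This should be fixed. It is not critical to the trial, because it affects one secondary endpoint.

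**What to change.** Before the treatment codes are released, amend SAP 9.2 for outcome (f) in one of two ways:

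1. Make the outcome the mean of the daily ratings in the 7 days before each visit, in line with Protocol F.2.4, and add a random subject-by-period intercept to model (2) for this outcome.
2. Analyse one mean per patient per period.

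Averaging alone is not sufficient. If daily values are kept instead, the subject-by-period intercept is still needed, the protocol's definition must be reconciled, and the SAP should say whether AR(1) runs on study day across the diary gaps.

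Write the added term for outcome (f) specifically, because model (2) also serves WOMAC-C, HADS and PROMIS Sleep Disturbance. HADS and PROMIS Sleep Disturbance are measured after Baseline only at weeks 6, 12, 18 and 24. With one value per period, such a term could not be separated from the residual.

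The cost is a short piece of SAP text and no new data. Confidence intervals for this outcome will be wider where shifts exist, and their coverage will be close to the stated 95%.
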